15.3 General Approach to Statistical Analyses

All confidence intervals and p-values will be two-sided and statistical significance at the 0.05 level.

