08/06/20	Updated time points for assessment of mediators to include baseline or randomization notification and 3 months only	Align with final protocol
08/06/20	Updated inclusion and exclusion criteria to align with final criteria in protocol in section 6.0	Finalized based on pilot study completion
08/06/20	Changed randomization stratification based on sex to be based on EHR data and not self-reported sex in baseline survey in section 8.0	Changed due to ability to ensure EHR variable is not missing
08/06/20	Changed description of coding of relatedness of SAEs in section 19.3 to: 1) related, 2) possibly related, 3) not related (it was: definitely, probably, possibly, definitely not	The 3-level coding specified is how it is described in DSMP
09/18/20	Added rural/medically underserved residency as stratum for randomization in section 8.0 and adjusted variable in section 14.0	In response to DSMB recommendation
09/18/20	Added assessment of MCID for two subscales of pain severity composite measure (MCID in pain intensity and MCID in pain-related interference) in sections 3.0 and 15.0	In response to DSMB recommendation
09/18/20	Modified analysis plan to handle clustering within health coach in sections 14.0 and 15.0	In response to DSMB recommendation
09/25/20	Specified one additional EHR-based inclusion criterion to be applied at KPWA site only: no opioid use disorder (OUD) ICD-10 codes in section 6.1	To ensure coordination with another HEAL study at KPWA site specifically treating those with pain and OUD

10/19/20	Corrected location of Essentia Health (not Iowa but Wisconsin) in section 1.0	Error in description
10/19/20	Removed physician chart review of hospitalizations at each site as part of systematic/routine SAE identification in EHR data. DSMB approved change via email. Aligned description of ad hoc SAE identification and review with DSMP in section 19.2	Hospitalization review was modification from original, peer-reviewed DSMP; had not been planned, budgeted or deemed necessary for this minimal risk study.

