14.0. Primary Effectiveness Analyses

Primary Outcome Statistical Hypothesis: Both active interventions (painTRAINER and virtual coach-led CBT-CP) are expected to result in a higher proportion of patients achieving MCID (30% reduction in overall BPI-SF score) in pain severity relative to those receiving usual care at 3-month follow-up (primary time point).

Secondary Time Point Statistical Hypotheses: Both active interventions (painTRAINER and virtual coach-led CBT-CP) are expected to result in a higher proportion of patients achieving MCID (30% reduction in overall BPI-SF score) in pain severity relative to those receiving usual care at the 6 and 12-month follow-ups (secondary time points).

Primary Outcome and Secondary Time Point Analyses: We will use modified Poisson regression^{20,21} fit using generalized estimating equations (GEE) to model the binary primary outcome, MCID in pain severity (30% reduction from baseline), 3 months (primary time point) and 6 and 12 months (secondary time points). We are employing modified Poisson (i.e., Poisson family with log link, but use robust standard errors to correct for mis-specified outcome variance) instead of logistic regression since the binary outcome is not rare and the estimate of interest is the relative risk. We will use a working independence correlation matrix and will calculate standard errors using the robust sandwich estimator to account for within-person and within-health coach correlation^{21,22} and account for the mis-specified mean-variance structure when using Poisson regression for a binary outcome.^{20,23} We will include interactions between each intervention and indicators of time (3, 6, 12 months) to estimate time-specific intervention effects; the primary comparisons will be between the interventions and usual care at 3 months (i.e., primary effectiveness will test the size of the intervention coefficient at the 3-months timepoint). We will adjust for baseline levels of pain severity, other stratification variables (sex, clinical site, and rural/medically underserved residency), and a priori variables predictive of outcome (multisite pain and co-occurring mental health condition). Specifically, we will fit the following mean model where Usual Care and 3 months are the reference groups:

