15.0. Secondary Effectiveness Analyses (Secondary Outcomes)

Secondary Outcomes (Aim1a) Primary Statistical Hypotheses: Those in both active intervention conditions will show greater improvements in overall pain severity, pain intensity (MCID and overall), pain-related interference (MCID and overall) and related quality of life outcomes (social role functioning, physical functioning, and patient global impression of change) relative to those receiving usual care at the 3-month follow-up.

Secondary Outcomes (Aim1a) Secondary Statistical Hypotheses: Those in both active intervention conditions will show greater improvements in overall pain severity, pain intensity (MCID and overall), pain-related interference (MCID and overall) and related quality of life outcomes (social role functioning, physical functioning, and patient global impression of change) relative to those receiving usual care at the 6- and 12-months follow-ups (secondary time points).

Secondary Outcomes (Aim 1a) Analyses: Aim 1a will examine the impact of the active interventions on secondary outcomes. Analyses of these outcomes will follow the same proposed approach as Aim 1. We will use linear regression for continuous outcomes and Poisson regression for binary and count outcomes. We will use GEE^{21,22} to estimate regression models for longitudinal data using an independence working correlation matrix. We will calculate all standard errors using the robust sandwich estimator^{21,22} to account for within-person and within-health coach correlation or any misspecified variance structures. We will include an interaction between intervention arms and time indicators, and the primary time point for all secondary analyses will be 3 months following randomization and will include as covariates baseline levels of pain severity and all stratification variables.

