Mediator (Aim 1c) Analyses: We will use mediation analyses to assess and quantify the effect of theory-based mediators (pain-catastrophizing, pain self-efficacy, perceived support). Mediators represent a causal pathway between the intervention and outcome. Mediation occurs when the intervention influences a variable (the mediator) that in turn subsequently influences the outcome variable. Controlling for a mediator variable causes the strength of relationship between intervention and outcome to be meaningfully reduced. Consistent with recommendations, we will conduct mediation analyses only for interventions that have significant impacts on the outcomes under consideration at 6 months. Primary mediation analyses will assess the effect of the potential mediators on the primary outcome at 6 months, MCID in pain severity, while explanatory secondary analyses will investigate mediator impacts on secondary outcomes at 6 months. We will conduct mediation analyses using the framework recommended by Baron and Kenney²⁴ but using more recent statistical methods developed to better quantify and decompose different aspects of the mediation effect.²⁵ We will run a separate set of mediator analyses for each intervention compared to usual care. We will illustrate our approach for the binary outcome, achieving MCID in pain severity at 6 months.

Our statistical approach for mediation analysis will be to first demonstrate an association between the interventions and the binary outcome, achieving MCID in pain severity at 6 months (step 1; Aim 1).

Step 1 Model:

$$\log(E(Y_i)) = \beta_0 + \beta_1 Int_i + \boldsymbol{\beta}_z \mathbf{Z}_i$$

where Y_i is the binary outcome achieve MCID in pain at 6 months for participant i ($i=1,\dots,n$), Int_i is 1 if the participant i is randomized to given intervention group and 0 otherwise and \mathbf{Z}_i is a vector of baseline adjustment covariates.

We will then demonstrate an association between the interventions and change in each mediator at 3 months (step 2). To do this, we will construct a regression model for each potential mediator under consideration, with the change between the value of the mediator recorded at 3 months and baseline as the dependent variable including a main effect for the intervention. We will do this for each potential mediator and include in the next step only those mediators that are associated with either intervention group with a p-value less than 0.10 (test based on β_{M1} below).

Step 2 Model:

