$$E(M_i) = \beta_{Mo} + \beta_{M1} Int_i + \beta_{Mz} Z_i$$

where M_i is the change in mediator of interest from baseline to 3 months for participant i and we will fit this model using linear regression.

The next step (step 3) will be to demonstrate the reduction of the intervention effect on the outcome after removing the effect of the mediator(s). To do this, we will construct a multi-mediator inverse probability weighted (IPW) regression model. This approach allows us to estimate the direct effect of the intervention after rebalancing the intervention and UC groups with respect to the mediators. The application of the IPW approach, as compared to the traditional approach of adjusting for multiple mediators, will allow us to more appropriately account for confounding between a mediator and the outcome both by additional mediators and by other measured variables. Specifically, we will first model the probability of receiving the active intervention given the change in mediators from baseline to 3 months (all mediators that were found associated with intervention in step 2) using logistic regression adjusting for potential baseline confounders (Step 3a).

Step 3a Model:

$$\text{logit}(E(Int_i)) = \beta_{Wo} + \beta_{WM} Msub_i$$

where $Msub_i$ is vector of the subset of mediators that are shown to be associated with the intervention group in Step 2. This model will be used to construct weights defined as the inverse of the estimated probability that each person was assigned to their intervention given their observed mediator value. Specifically, the weights will be:

$$w_i = \begin{cases} \{\exp(\hat{\beta}_{Wo} + \hat{\beta}_{WM} Msub_i)\}/(1 + \exp(\hat{\beta}_{Wo} + \hat{\beta}_{WM} Msub_i))\}^{-1} & \text{for } Int_i = 1 \\ \{1 - \exp(\hat{\beta}_{Wo} + \hat{\beta}_{WM} Msub_i)\}/(1 + \exp(\hat{\beta}_{Wo} + \hat{\beta}_{WM} Msub_i))\}^{-1} & \text{for } Int_i = 0 \end{cases}$$

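### SAP 16.0 Step 2 states no allowance for within-coach correlation; fitted as written, the coach-versus-usual-care mediator test at nominal 10% would run at about 14% to 28% for an assumed ICC of 0.01 to 0.05

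*SAP*

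**What the plan says.** SAP 16.0 runs mediation one program at a time: "We will run a separate set of mediator analyses for each intervention compared to usual care". Step 2 models the change in each mediator (catastrophizing, self-efficacy, perceived support) from baseline to 3 months on the arm indicator and baseline covariates. On fitting it says only that "we will fit this model using linear regression". The analysts will then "include in the next step only those mediators that are associated with either intervention group with a p-value less than 0.10". Under Protocol 15.3, "All confidence intervals and p-values will be two-sided".

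No coach term, random effect, clustered variance or robust variance appears in the mediator text. Two other sections differ:

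- SAP 14.0 (primary outcome) says that the analysts "will calculate standard errors using the robust sandwich estimator to account for within-person and within-health coach correlation".
- SAP 15.0 (secondary outcomes), which includes linear regression of continuous outcomes, uses the sandwich estimator "to account for within-person and within-health coach correlation or any misspecified variance structures".

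The SAP's change table describes the scope of this provision: "Modified analysis plan to handle clustering within health coach in sections 14.0 and 15.0". Section 16.0 is not listed. Elsewhere the SAP says so when an approach carries over: the moderator paragraph of 16.0 follows the general Aim 1 approach, and 17.0 points back to 15.0. Step 1 of the mediation is labelled as Aim 1. Step 2 has no such link, and Protocol 15.7 refers the reader to the SAP for mediator detail.

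**The concern.** Participants are randomized individually, but each person in the coach arm has an assigned coach who delivers the sessions one-on-one (Protocol 10.1.2). Protocol 6.2 puts the coaching staff at about 12. If coaches differ, outcomes in that arm are correlated within coach, and a regression that treats every participant as independent gives a standard error that is too small for the coach-versus-usual-care comparison.

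Step 2 does two jobs. It is the stated evidence that a program moves a mediator, and it decides which mediators enter the Step 3 weights. An understated standard error would credit the coach program with moving mediators more often than the 10% rule implies. The painTRAINER comparison would not be affected in the same way, although Aim 1c reports the two programs side by side.

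**Working it through.** **Inputs from the documents.** Analysed per arm: 621 (SAP 5.0). Coaches: about 12 (Protocol 6.2). Test: two-sided, p < 0.10 (SAP 16.0, Protocol 15.3). Allocation: equal (SAP 8.0).

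**Assumptions.** Equal coach loads, so m = 621/12 = 51.75 participants per coach. Clustering in the coach arm only. The documents give no ICC, so a range is shown.

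**Formulas.**

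- Design effect in the coach arm: DE = 1 + (m − 1) × ICC. Usual care has DE = 1.
- True variance of the arm difference divided by the variance that unclustered regression reports: R = (1 + DE)/2.
- True level of the nominal 10% test: 2 × [1 − Φ(1.645/√R)].

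**Results, coach arm versus usual care.**

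| ICC | DE | R | √R | True level |
|---|---|---|---|---|
| 0 | 1.00 | 1.00 | 1.00 | 10.0% |
| 0.005 | 1.25 | 1.13 | 1.06 | 12.1% |
| 0.01 | 1.51 | 1.25 | 1.12 | 14.2% |
| 0.02 | 2.02 | 1.51 | 1.23 | 18.0% |
| 0.05 | 3.54 | 2.27 | 1.51 | 27.5% |

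The first row returns the plan's own 10%. Simulation (8,000 trials per setting, 12 coaches of 51) gave 13.9%, 18.4% and 28.0% at ICC 0.01, 0.02 and 0.05.

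**Sensitivity, same formula, ICC 0.01 to 0.05.**

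- 8 coaches: 16% to 34%.
- 20 coaches: 13% to 21%.
- 777 per arm with 12 coaches: 15% to 31%.
- 400 per arm with 12 coaches (an assumed lower number of change scores): 13% to 22%.

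**The selection rule taken literally.** SAP 16.0 keeps a mediator that passes for either program. The two test statistics share the usual-care arm, so with equal arms and no clustering their correlation is 0.5. The chance that at least one exceeds 1.645 in absolute value is then 17.5% for a null mediator by the bivariate normal calculation; the simulation gave 16.2%. Giving the coach statistic variance R and keeping the covariance at 0.5 yields 21.4% at ICC 0.01 and 33.8% at ICC 0.05; the simulation gave 21.2% and 34.6%.

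**What clustering on coach achieves** (simulated level of the 10% test, 12 coaches, each usual-care participant a cluster of one).

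| ICC | Plain sandwich, normal reference | k/(k − 1) correction, Satterthwaite t |
|---|---|---|
| 0.01 | 11.6% | 10.1% |
| 0.02 | 12.6% | 10.8% |
| 0.05 | 12.8% | 9.8% |

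Here k is the number of coaches.

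**The case against.** The strongest reply is that Step 2 names a mean model and no standard-error method. SAP 15.0 also says linear regression and then specifies the sandwich separately, so in this plan the phrase need not mean model-based errors. The authors may have intended the 15.0 variance throughout, and the Aim 1 label on Step 1 may well bring the Aim 1 variance into that step. This stands in part: a reader might infer that the plan has chosen a test that ignores clustering, and the documents do not show that. They show that no allowance is stated for Step 2, in a section without the carry-over wording used elsewhere. An analyst following the text would have no instruction to cluster.

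Other points also stand:

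- The ICC is assumed. Manuals, proficiency scoring and continuing fidelity review (Protocol 10.4) are meant to limit differences between coaches.
- Perceived support has its baseline on a mailed paper survey (Protocol 11.2), so fewer than 621 change scores per arm are plausible, which lowers the rate. Conversely, the figure of about 12 may include painTRAINER support staff; fewer coaches would raise it.
- Staff also telephone painTRAINER participants (Protocol 10.1.1), so some shared-staff correlation there cannot be excluded.
- Sections 14.0 and 15.0 state no small-sample correction, so asking for one in Step 2 goes beyond consistency with them.

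None of these supplies the missing statement for Step 2.

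**Conclusion.** The point holds as a gap in the stated Step 2 analysis. If the model is fitted as written, the single coach-versus-usual-care test would run at about 14% (ICC 0.01), 18% (ICC 0.02) or 28% (ICC 0.05) instead of 10%, given 12 coaches of equal load, 621 analysed per arm and clustering in the coach arm only.

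Two stronger readings are not supported. First, 14% to 28% is not the error rate of the rule that selects mediators: read literally, that rule passes a null mediator about 16% to 18% of the time with no clustering at all, and about 21% to 35% with it. Second, the trial's main conclusions are not in question. SAP 14.0 already allows for coach correlation in the primary analysis. Mediation belongs to a secondary aim and runs only for interventions with a significant 6-month effect, and the 0.10 cut-off is a lenient screen. The effect on the Step 3 weighted estimates was not computed, so no claim is made about its size.

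**What to change.** Add to SAP 16.0 that the Step 2 coach-versus-usual-care test uses standard errors clustered on health coach, as in 14.0 and 15.0, with each usual-care participant as their own cluster, and that the p < 0.10 rule applies to that test. Preferably specify a small-sample correction with a Satterthwaite t reference, since the plain sandwich does not quite restore 10% with about 12 coaches. State the same clustered variance for the coach comparisons in Step 1 and in the weighted Step 3 model.

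This is a wording change and one model option. Coach identity is already needed for 14.0 and 15.0, so no new data are required. The price is lower power for the coach arm's mediator tests if coaches do differ.

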We will then use these weights to fit a weighted regression model for the binary outcome, achieving MCID in pain severity at 6-months, applying the same mean model as Step 1 except using the weights w_i . In this approach, the weights in essence “weigh out” the effect of the mediator at 3 months. Comparing the estimates of the intervention effect in the weighted and unweighted models will allow us to estimate how much the intervention effect on the outcome can be explained by each potential mediator. We will further be able to quantify the amount of effect explained by each mediator independent of the other mediators.

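### SAP Step 3a promises mediation weights adjusted for baseline confounders, but its model, its weight definition and both weight formulas contain only the mediators

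*SAP*

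**What the plan says.** SAP section 16.0 sets out the mediation analysis in steps, run separately for each intervention against usual care.

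- Step 1 regresses 6-month MCID on arm and Z, where Z "is a vector of baseline adjustment covariates". Step 2 regresses each mediator's change on arm and Z.
- Step 3 states "we will construct a multi-mediator inverse probability weighted (IPW) regression model". Weighting is preferred to ordinary adjustment because it can "account for confounding between a mediator and the outcome both by additional mediators and by other measured variables".
- Step 3a models the probability of being in the intervention arm given the mediator changes, "using logistic regression adjusting for potential baseline confounders (Step 3a".
- The printed Step 3a logit has an intercept and Msub only. Msub "is vector of the subset of mediators that are shown to be associated with the intervention group in Step 2".
- The weight is the "inverse of the estimated probability that each person was assigned to their intervention given their observed mediator value". Both formula branches (Int = 1 and Int = 0) contain only the intercept and Msub.
- The weighted outcome model is fitted by "applying the same mean model as Step 1 except using the weights", so Z stays in that regression.
- The weighted and unweighted intervention effects are then compared, and the plan also undertakes to "quantify the amount of effect explained by each mediator independent of the other mediators".

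Protocol section 15.7 refers to the SAP for the mediator methods and does not settle the point.

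**The concern.** Step 3a contradicts itself. One sentence puts baseline confounders in the weights; the equation, the definition of its regressors, the verbal definition and both formulas leave them out. Steps 1 and 2 print Z, so its absence here is not a habit of notation. The sentence cannot be programmed as it stands either, because its confounders are not listed.

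The mediated share is what Aim 1c reports. Two analysts following the same section could report different shares, and the choice between them could be made after seeing the data. The printed version also lacks the property for which the SAP chose weighting, namely control of confounding by measured variables.

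**Working it through.** **Why Z in the outcome model does not repair the weights.** Take randomized arm A and one baseline covariate C (part of Z), with mediators M_k = a_k·A + l_k·C + e_k, each with SD 1 within arm. Let log P(Y) = b0 + d·A + Σ b_k·M_k + c·C. C is independent of A by randomization, but not at a fixed value of the mediators. Weights built on the mediators alone therefore leave C different between arms by −l′S⁻¹a, where S is the within-arm mediator covariance. Adjusting the outcome for C uses the slope c + Σ b_k·l_k instead of c, so the estimated direct log RR is off by

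shift = (Σ b_k·l_k) × (l′S⁻¹a).

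With one mediator this is R²·a·b, where R² = l² is the share of mediator variance that C explains. The shift is zero if either factor is zero, and with several mediators it can take either sign.

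**Inputs.** The usual-care rate of 15% comes from SAP section 5.0, where it is the assumed 3-month rate. The rest are assumptions, since the documents give no figures: direct RR 1.20 (log 0.1823), c = 0.4, no interactions, and the a, b and l values below.

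**One mediator, b = 0.4.** For a = 0.3 the mediated log RR is 0.3 × 0.4 = 0.12 and the true share is 0.12/(0.1823 + 0.12) = 39.7%. With R² = 9% the printed weights give 0.12 × 0.91 = 0.1092, a share of 0.1092/0.3023 = 36.1%. Simulated shares (4 runs of 1,000,000), printed weights against Z in the weights:

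| Z explains | arm shift 0.3 SD | arm shift 0.5 SD |
|---|---|---|
| 4% | 38% vs 40% | 50% vs 52% |
| 9% | 36% vs 40% | 47% vs 52% |
| 25% (upper end) | 30% vs 40% | 39% vs 52% |

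**Two mediators, Z explaining 9% of each (|l| = 0.3).**

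- Loadings of the same sign, a = 0.3/0.3, b = 0.3/0.3: Σbl = 0.18 and l′S⁻¹a = 0.6 × 0.3/1.09 = 0.1651, so the shift is 0.0297. The share is (0.18 − 0.0297)/0.3623 = 41.5% against 49.7%.
- Opposite loadings, same values: Σbl = 0, no bias, 49.7% both ways.
- Opposite loadings, a = 0.2/0.5, b = 0.4/0.1: Σbl = 0.09 and l′S⁻¹a = −0.0826, so the shift is −0.0074. The share is (0.13 + 0.0074)/0.3123 = 44.0% against 41.6%, an overstatement. At 25% it is 47% against 42%.

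**Three mediators, Z explaining 1–9% of each.** I took 40,000 draws at each residual correlation of 0, 0.3 and 0.5, with a 0.1–0.5 and b 0.1–0.4. The widest 5th–95th percentile range is 1.3 to 9.9 points understated when all loadings share a sign, and 2.9 understated to 1.1 overstated when signs are mixed.

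**Check of the formula.** It was compared with simulation in nine settings. Examples, formula against simulated shift: 0.0048 vs 0.0048, 0.0180 vs 0.0187, 0.0297 vs 0.0303, −0.0074 vs −0.0072, 0.0282 vs 0.0280. A separate simulation used other inputs (150,000 people, true direct log RR 0.25) and kept the covariate in the outcome model. It gave 0.272 with the printed weights against 0.256 with the covariate in the weights, and 0.295 against 0.253 for a stronger covariate. The two agreed when the covariate did not affect the mediator.

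**Against sampling error, 621 per arm (2,000 trials).** The SD of the mediated log RR is 0.028 to 0.043. With one mediator the bias is 0.2 SD (Z explains 4%) or 0.4–0.5 SD (9%). In the three two-mediator cases it is 0.8, 0 and −0.2 SD.

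**The mediator's own baseline.** The Aim 1 covariates in SAP section 14.0 do not include baseline catastrophizing or self-efficacy. Suppose the outcome depends on L3 − θ·M0 (3-month score minus θ times baseline, both with SD 1 and correlation r) and the weights balance only the change L3 − M0. The fraction of the mediated effect captured is (1 − r)(1 + θ)/[2(1 − r)] = (1 + θ)/2, whatever r is. For θ = 1 (change only) nothing is lost. For θ = 0.5 the share is 0.75 × 0.12/0.3023 = 30% against 40% (39% vs 52% at shift 0.5). In the boundary case θ = 0 it is 20% against 40% (26% vs 52%).

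**The case against.** The SAP states its intent twice, in the Step 3a sentence and in the reason given for weighting, and it presents the equations as an illustration. A careful statistician would probably add Z, which section 14.0 all but lists. On that view this is an incomplete equation.

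The practical loss can also be small. In a one-mediator simulation at 621 per arm, the root mean squared error of the mediated log RR (printed weights vs Z in the weights) was 0.0280 vs 0.0284 when Z explained 4% and the arm shift was 0.3 SD. At 9% it was 0.0301 vs 0.0294 for shift 0.3 and 0.0411 vs 0.0390 for shift 0.5, a loss of 2–5%. Only at 25% did the two separate clearly (0.0383 vs 0.0298). Complete mediation data will probably come from fewer than 621 per arm, which makes the bias smaller relative to noise.

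The own-baseline point is a separate matter. Leaving those scores out does no harm under the SAP's change-score hypothesis. If Z correlates 0.5 or 0.7 with the baseline score and is in the weights, the boundary-case share rises from 20% to 24% or 30%, against 40–42% with the score added.

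These points limit the size and stand as limits. They do not remove the contradiction: Z is never identified as the Step 3a confounders, and code that follows the printed formulas gives a different answer from code that follows the sentence.

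**Conclusion.** The concern holds and is minor. That Step 3a contradicts itself is a matter of text and depends on no simulated figure. As printed, the weights bias the direct effect and the mediated share when baseline covariates predict mediator change. The exception is when the effects across mediators cancel.

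The size is conditional on the assumed inputs: about 2 to 5 percentage points understated with one mediator and covariates explaining 4–9% of its variance, and about 10 to 13 points at 25%. With the several mediators the SAP plans, the direction cannot be known in advance. The reach is Aim 1c only, and within it only an intervention with a significant 6-month effect. The primary analysis is not affected.

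**What to change.** Add a named baseline vector X to the Step 3a logit, to the verbal definition and to both weight formulas, so that the weight is the inverse of P(own arm | Msub, X). X should contain at least:

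- the Aim 1 covariates of SAP section 14.0: baseline pain severity, sex, site, rural/medically underserved residency, multisite pain and co-occurring mental health condition;
- baseline catastrophizing and self-efficacy scores, as protection in case the outcome depends on level as well as change.

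X should not contain the perceived-support score taken at notification of assignment, because it is measured after randomization (SAP section 4.0). Deleting the adjustment phrase instead would remove the contradiction but keep the bias, and the stated reason for weighting would then have to go too.

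The cost is SAP wording and extra terms in one logistic model, with no new data. The weights become somewhat more variable. With one mediator the effective sample size falls by at most about 2.4 points. With three mediators, eight covariate columns and two baseline scores at 621 per arm, it falls from 97% to 95% (arm shifts 0.2 SD), from 94% to 89–90% (0.3 SD) or from 81% to 68–71% (0.5 SD). The loss is small unless the arms differ strongly on all three mediators.

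### SAP 16.0 promises a separate share for each mediator, but its single joint weight yields only the joint mediated share when two or more mediators are retained

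*SAP*

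**What the plan says.** The method is in SAP 16.0, Mediator (Aim 1c) Analyses. Protocol 15.7 names the same mediators and the 6-month outcome, adds no method, and refers to the SAP.

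- Scope: "We will use mediation analyses to assess and quantify the effect of theory-based mediators (pain-catastrophizing, pain self-efficacy, perceived support"). Each intervention is compared with usual care separately.
- First condition: "we will conduct mediation analyses only for interventions that have significant impacts on the outcomes under consideration at 6 months".
- Second condition (Step 2): the plan will "include in the next step only those mediators that are associated with either intervention group with a p-value less than 0.10".
- Step 3: "we will construct a multi-mediator inverse probability weighted (IPW) regression model". The only regressor in the Step 3a weight model "is vector of the subset of mediators that are shown to be associated with the intervention group in Step 2". Each person's weight is the "inverse of the estimated probability that each person was assigned to their intervention given their observed mediator value".
- Estimate: the Step 1 outcome model is refitted with these weights. "Comparing the estimates of the intervention effect in the weighted and unweighted models will allow us to estimate how much the intervention effect" is explained, and the sentence ends by attributing this to each potential mediator.
- Closing claim: "We will further be able to quantify the amount of effect explained by each mediator independent of the other mediators".

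No single-mediator, leave-one-out, sequential or path-specific weight is defined. The SAP does not say whether one mediator may act on another, or whether the shares should add to a total.

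**The concern.** The last two sentences of the section claim a property that the preceding steps do not have. A weight built from the whole mediator vector balances all retained mediators between arms at once. The change in the intervention effect is then what those mediators carry together, and nothing in the procedure divides it.

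Aim 1c concerns the role of three named mechanisms, so per-mediator figures are what readers would look for. To produce them, the analyst would have to devise an additional procedure after the data are in. The candidates can give very different answers from the same data, and the SAP gives no basis for choosing among them.

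**Working it through.** **No plan figure to reproduce.** The documents give no mediated share and no formula for one. The check is therefore of what the written steps can deliver, followed by an illustration under stated assumptions.

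**Step 1: count what the method produces.** For each intervention there is one unweighted effect (Step 1 model) and one weighted effect (Step 3). Taking the share as 1 − log RR(weighted) / log RR(unweighted), this is one number. With one retained mediator, that number is the mediator's share. With two or three, it is their joint share, and no per-mediator number exists.

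**Step 2: what happens if the gap is filled.** These inputs are assumptions, not from the documents:

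- three normal mediators, each shifted by d = 0.3 SD by treatment;
- common within-arm correlation ρ;
- equal coefficients b on log risk;
- no mediator-outcome confounding from outside the set;
- no mediator causing another.

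The SAP's design rates are used for scale: 15% under usual care (both set-ups) and 22.5% under intervention (60% set-up below). They are 3-month values, applied here to 6 months.

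The joint share is J = 3bd / log RR.

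- *Single-mediator weights.* Balancing one mediator leaves each of the others with a residual shift of d(1 − ρ). The share credited to that one is (J/3)(1 + 2ρ), so the three sum to J(1 + 2ρ).
- *Leave-one-out weights* (joint share minus the share from the other two). Given the other two, the residual shift is d(1 − ρ)/(1 + ρ). The three sum to J(1 − ρ)/(1 + ρ).

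Example at ρ = 0.5: multipliers are 1 + 1 = 2.00 and 0.5/1.5 = 0.33. With J = 69%, the sums are 138% and 23%, that is 46% or 8% per mediator.

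Two simulated set-ups agree with these formulas. One has J = 60% (RR 1.5, share on the log RR scale, 200,000 per arm). The other has J = 69% (RR about 1.38, share on the risk-difference scale, at least 1,000,000 people).

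| ρ | Single: multiplier | Sum, J = 60% | Sum, J = 69% | Leave-one-out: multiplier | Sum, J = 60% | Sum, J = 69% |
|---|---|---|---|---|---|---|
| −0.3 | 0.40 | 24% | not run | 1.86 | 112% | not run |
| 0 | 1.00 | 60% | 69% | 1.00 | 60% | 69% |
| 0.1 | 1.20 | 72% | 83% | 0.82 | 49% | 56% |
| 0.3 | 1.60 | 96% | 108–113% | 0.54 | 32% | 37% |
| 0.5 | 2.00 | 120% | 138% | 0.33 | 20% | 23% |
| 0.7 | 2.40 | 143% | 165% | 0.18 | 11% | 12% |

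The joint share from the SAP's own weights stayed on target throughout: 59.4% to 60.3% against a true 60%, and 68% to 70% in the other set-up.

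**Step 3: one active mediator, two inert, ρ = 0.5, J = 60%.** Single-mediator weights credit each inert mediator with ρ × 60% = 30% (simulated: 30%). Leave-one-out weights give the inert ones 0%, but the active one only 60% × 0.33 = 20%.

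**Step 4: trial size.** With 621 per arm (SAP 5.0), ρ = 0.5 and J = 60%, 552 of 600 replicates had a significant total effect. Among these, the median joint share was 58% (5th to 95th percentile 37% to 89%). The median single-mediator sum was 116% and the median leave-one-out sum 19%.

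**The case against.** The strongest reply has four parts.

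**The error figures come from procedures that the SAP does not contain.** This stands. A reader might infer that Aim 1c will report shares that add to far more or less than the mediated part. The documents do not support that, because they fix no per-mediator weights and promise no additivity. The table shows what could follow from an unstated choice. It does not show what the plan will produce.

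**The size rests on a correlation that the documents do not give.** This also stands. At ρ = 0 there is no error, and at 0.1 the sums are off by about 20%. The relevant correlation is between change scores. Perceived support is two study-developed items whose baseline comes from a paper survey mailed with the arm notification (Protocol 11.2), so a high value cannot be presumed.

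**Mechanisms need not be ranked wrongly.** A reader might infer misranking, but it is not shown, and the SAP does not say it will rank mediators. Equal mediators cannot reveal misranking. With true shares 40/20/0 and ρ = 0.5, single-mediator weights give 40 + 10 = 50, 20 + 20 = 40 and 20 + 10 = 30. Leave-one-out weights give about 13, 7 and 0 (one third of each). Sizes are distorted but the order holds.

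**Leave-one-out is a legitimate reading of independence.** In part. It is a well-defined increment and gives inert mediators nothing, but it is not written down, and it shrinks the active mediator from 60% to 20% at ρ = 0.5. The SAP justifies multi-mediator weighting by the need to handle confounding through the other mediators, which itself tells against single-mediator weights.

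None of these points supplies the missing procedure or makes the joint weight divisible.

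**Conclusion.** The point holds as a mismatch between claim and method. As written, Step 3 identifies the joint mediated share per intervention. The two sentences that close the section attribute to it a per-mediator result that it cannot give once two or more mediators are retained. A blanket statement that per-mediator effects cannot be estimated would go too far: additional weight models could target them under a stated estimand and stated causal assumptions.

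The issue arises only if the intervention has a significant 6-month effect and at least two mediators pass p < 0.10. Its numerical size is conditional on the unknown correlation and on the analyst's choice of weights: nil at zero correlation, modest at 0.1, and large from about 0.3 upward or with clearly negative correlation.

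Protocol 3.4 lists the mediators under exploratory objectives. The consequence is confined to how Aim 1c is interpreted.

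**What to change.** In SAP 16.0:

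1. Name the joint share from the multi-mediator weights, with an interval (for example by bootstrap), as the Aim 1c estimate for each intervention.
2. In the sentence comparing weighted and unweighted models, replace the reference to each potential mediator with the retained mediators jointly.
3. Delete the closing sentence. Alternatively, replace it with a defined per-mediator estimand, the weights that estimate it, and the assumptions it needs about causal order or the absence of effects of one mediator on another.
4. Label any single-mediator results as descriptive, overlapping shares that need not sum to the joint share.

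Deleting only the closing sentence would leave the same claim in the one before it.

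Cost: SAP wording, plus the interval. The joint estimate is already planned and no new data are needed. The price is a more modest claim about individual mechanisms.
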